#### **4.2.13.2 Derivations**

Time from randomisation will be calculated as date of  $K^+$  - date of randomisation + 1.

#### **4.2.13.3 Handling of Dropouts and Missing Data**

All available  $K^+$  measurements up to the date of rescue therapy for HK will be used in the MMRM. Measurements after rescue therapy starts are assumed to be missing at random and that  $K^+$  measurements would behave similarly to other participants in the same treatment group with similar covariate values.

#### **4.2.13.4 Primary Analysis of Exploratory Endpoint #5**

A MMRM will be fitted in the FAS with  $K^+$  measurements as the dependent variable and randomised treatment group (reference level SoC), time from randomisation, country and the interaction of treatment group by time from randomisation with random effects for participant, intercept and slope. The covariance structure will be unstructured. The coefficient estimates, standard error, 95% CI for coefficient estimates, and p-values will be reported. The model assumptions will be assessed by plotting a histogram of the model residuals and a scatter plot of the model residuals versus predicted values.

#### **4.2.13.5 Sensitivity Analyses of the Exploratory Endpoint #5**

Providing there are sufficient participants within each covariate to support the analysis, an alternative population level summary using the FAS population where the MMRM analysis will include randomised treatment group and the following baseline variables: age (as a cubic spline), sex, presence of heart failure, diabetes, RAASi use, CKD stage and baseline  $K^+$  (mild HK defined by  $5.0 < K^+ \leq 5.5$  and moderate/severe HK defined by  $5.5 < K^+ \leq 6.5$  mmol/L) as independent variables. Baseline variables will be defined as described in section 4.1.6.1.

#### **4.2.13.6 Supplementary Analyses of the Exploratory Endpoint #5**

Not Applicable.

#### **4.2.13.7 Subgroup Analyses**

Not Applicable.

#### **4.2.14 Exploratory Endpoint #6 (Number of hospital admissions with HK)**

*Number of hospital admissions with HK as a contributing factor at any time post-discharge up to 180 days.*

##### **4.2.14.1 Definition**

- Population: Full analysis set
- Endpoint: Number of hospital admissions with HK as a contributing factor, at any time post-discharge up to 180 days.

- Intercurrent event strategy: Participants who discontinue treatment, use rescue therapy for HK, have RAASi down-titration (including discontinuation), experience all-cause death or loss to follow-up prior to 180 days post-discharge will have all available hospital admission and ED visit data used irrespective of the intercurrent event (treatment policy strategy).
- Population level summary: Mean number of hospital admissions with HK as a contributing factor, by randomised treatment group will be summarised. Negative binomial regression model with randomised treatment group as a main effect and including duration of time in study as an offset. The incidence rate ratio (SZC/SoC), along with 95% confidence intervals and two-sided p-values will be displayed.

#### **4.2.14.2 Derivations**

For each participants the total number of separate hospital admissions with HK as a contributing factor up to 180 days will be calculated. Hospital admissions will be calculated as separate admissions if start and stop dates of admission do not overlap. If hospital admissions are missing a start, stop date or both then they will be calculated as separate admissions. Hospital admissions after 180 days will not be counted.

#### **4.2.14.3 Handling of Dropouts and Missing Data**

All available data on hospital admissions are to be used irrespective of intercurrent events. For the primary analysis, no adjustment is made for dropout but the sensitivity of the results to this approach are investigated using a sensitivity analysis in section 4.2.14.5.

#### **4.2.14.4 Primary Analysis of Exploratory Endpoint #6**

A descriptive summary (Mean, SD, Median, Range) of the number of hospital admissions with HK as a contributing factor will be presented by randomised treatment group in the FAS. A negative binomial regression model will be conducted with the number of hospital admissions with HK as a contributing factor as the dependent variable and randomised treatment group (reference level SoC) as the independent variable. The duration of time per participant in study is calculated until the earliest of loss to follow-up or 180 days post-discharge and will be included in the model as an offset term. The incidence rate ratio (SZC/SoC), along with 95% CIs and two-sided p-values will be displayed. To check the model assumptions, that the conditional means are not equal to the conditional variance, the dispersion parameter will be checked by fitting a Poisson model and by performing a chi-squared test with 1 degree of freedom with a test statistic of twice the difference in log likelihoods.

#### **4.2.14.5 Sensitivity Analyses of the Exploratory Endpoint #6**

Two sensitivity analyses will be conducted for this exploratory endpoint:

- Providing there are sufficient participants within each covariate to support the analysis, an alternative population level summary using the FAS population where the negative

binomial regression model will include randomised treatment group, duration of time in study as an offset and the following baseline variables: age (as a cubic spline), sex, participant recruitment country, presence of heart failure, diabetes, RAASi use, CKD stage, and baseline  $K^+$  (mild HK defined by  $5.0 < K^+ \leq 5.5$  and moderate/severe HK defined by  $5.5 < K^+ \leq 6.5$  mmol/L) as independent variables. Baseline variables will be defined as described in section 4.2.2.6.

- A sensitivity analysis will be conducted using the mean cumulative count method (MCC) (Dong et al, 2015) if a greater than 10% difference by treatment arm in the proportion who are lost to follow-up is observed. The MCC method reflects a summarisation of all events that occur in a population by a given time. The recurring event in this analysis will be hospital admission with HK as a contributing factor. The MCC will be performed by randomised treatment group in the FAS and an estimate (95% CI) of the MCC at 90 and 180 days post discharge will be presented. A figure of the MCC by randomised treatment group with 95% CI will also be displayed. SAS Code to conduct an MCC analysis is described in sections 7.1 and 7.2.

#### **4.2.14.6 Supplementary Analyses of the Exploratory Endpoint #6**

Not Applicable.

#### **4.2.14.7 Subgroup Analyses**

Not Applicable.

### **4.2.15 Exploratory Endpoint #7 (LOS for hospitalisation with HK)**

*Total length of stay (LOS) for hospitalisations (including multiple hospitalisations) with HK as a contributing factor in each arm at any time post-discharge up to 180 days.*

#### **4.2.15.1 Definition**

- Population: Full analysis set
- Endpoint: Total LOS for hospitalisations (including multiple hospitalisations) with HK as a contributing factor in each arm at any time post-discharge up to 180 days.
- Intercurrent event strategy: Participants who discontinue treatment, use rescue therapy for HK, experience all-cause death, have RAASi down-titration (including discontinuation) or loss to follow-up prior to 180 days post-discharge will have all available hospital admission data used irrespective of the intercurrent event (treatment policy strategy). Hospital admissions which extend beyond 180 days post-discharge will be truncated at 180 days post-discharge.
- Population level summary: Continuous variable summary (mean and median) of total LOS with HK as a contributing factor, by randomised treatment group. A Wilcoxon rank-sum test by randomised treatment group will be used to calculate a two-sided p-value.

#### **4.2.15.2 Derivations**

LOS will be calculated using the hospital admission details eCRF with the adjudication committee determination of whether HK was a contributing factor. Each hospital duration will be calculated as the number of days: (Min(Stop date of admission, Randomisation date + 180) – Start date of admission + 1) and the total duration per participant will be calculated as the sum of all relevant hospital admissions.

#### **4.2.15.3 Handling of Dropouts and Missing Data**

All available data on hospital admissions are to be used irrespective of intercurrent events, no adjustment is made for dropout.

#### **4.2.15.4 Primary Analysis of Exploratory Endpoint #7**

The total duration of LOS with HK as a contributing factor will be summarised as a continuous variable (mean, SD, median, range) by randomised treatment group in the FAS. A Wilcoxon rank-sum test by randomised treatment group will be used to calculate a two-sided p-value.

#### **4.2.15.5 Additional Analyses of the Exploratory Endpoint #7**

Not Applicable.

#### **4.2.15.6 Subgroup Analyses**

Not Applicable.

### **4.2.16 Exploratory Endpoint #8 (LOS for all-cause hospitalisation)**

*Total LOS for all-cause hospitalisations (including multiple hospitalisations) in each arm at any time post-discharge up to 180 days.*

#### **4.2.16.1 Definition**

- Population: Full analysis set
- Endpoint: Total LOS for all-cause hospitalisations (including multiple hospitalisations) in each arm at any time post-discharge up to 180 days.
- Intercurrent event strategy: Participants who discontinue treatment, use rescue therapy for HK, experience all-cause death, or loss to follow-up prior to 180 days post-discharge will have all available hospital admission data used irrespective of the intercurrent event (treatment policy strategy). Hospital admissions which extend beyond 180 days post-discharge will be truncated at 180 days post-discharge.
- Population level summary: Continuous variable summary (mean and median) of total LOS of all-cause hospitalisation, by randomised treatment group. A Wilcoxon rank-sum test by randomised treatment group will be used to calculate a two-sided p-value.

#### **4.2.16.2 Derivations**

LOS will be calculated using the hospital admission details eCRF. Each hospital duration will be calculated as (Min(Stop date of admission, Randomisation date + 180) – Start date of admission + 1) and the total duration per participant will be calculated as the sum of all hospital admissions.

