#### **4.2.5.2 Derivations**

For each participant the total number of separate all-cause hospital admissions or ED visits with HK as a contributing factor up to 180 days will be calculated. Hospital admissions and ED visits will be calculated as separate admissions if start and stop dates of admission do not overlap. If hospital admissions or ED visits are missing a start, stop date or both then they will be calculated as separate admissions. Hospital admissions or ED visits started after 180 days will not be counted.

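### The length-of-stay formula lacks the start-date and overlap rules of the count endpoints, so late admissions can yield negative days and overlapping records count days more than once (exploratory endpoints #7 and #8).

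*SAP*

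**What the plan says.** Exploratory endpoints #7 (stays with HK as a contributing factor) and #8 (all-cause stays) use the same derivation. Each stay is "Min(Stop date of admission, Randomisation date + 180) – Start date of admission + 1". For #8, "the total duration per participant will be calculated as the sum of all hospital admissions" (SAP 4.2.16.2). For #7 the sum runs over the admissions that are relevant: "the total duration per participant will be calculated as the sum of all relevant hospital admissions" (SAP 4.2.15.2).

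The scope statement for #8 is "Total LOS for all-cause hospitalisations (including multiple hospitalisations) in each arm at any time post-discharge up to 180 days" (SAP 4.2.16.1), and the only boundary rule is "Hospital admissions which extend beyond 180 days post-discharge will be truncated at 180 days post-discharge". Section 4.2.15.1 has equivalent wording for #7.

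The count endpoints, built on the same kind of records, go further. Section 4.2.5.2 states "Hospital admissions and ED visits will be calculated as separate admissions if start and stop dates of admission do not overlap" and leaves out admissions and ED visits that begin after 180 days; 4.2.8.2 repeats both rules. Section 4.2.14.2 has the overlap rule for hospital admissions and adds "Hospital admissions after 180 days will not be counted".

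Admission data are still collected after day 180: the protocol's Schedule of Activities includes them at the follow-up visit (Visit 11), which SAP Table 4 places at EOT+4 to EOT+10.

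**The concern.** A formula that caps the end of a stay but not its beginning fails once the beginning lies past the cap. The stay then has a negative length, and because records are summed, the negative days cancel genuine ones. A participant whose only admission is late should have a total of 0. With a negative total, that participant is ranked ahead of everyone who was never admitted.

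Separately, each record counts both its first and last day, and records are simply added. Any calendar day covered by two records is therefore counted twice.

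The SAP foresees both situations for the counts but not for length of stay. The two sets of results could disagree: one late admission could add 0 to the count and a negative number to the days. At stake is the credibility of two resource-use summaries, in a trial whose rationale includes healthcare resource utilisation.

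**Working it through.** The plan states no figure for these endpoints, so there is none to reproduce. I evaluated the formula on example dates. R is the randomisation date; offsets R+n avoid ambiguity, because SAP 3.3.1 numbers the randomisation date as Day 1 (R+180 is study Day 181).

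**Late starts.** For any stay that starts after R+180, the result is 180 - start + 1:

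- R+180: 180 - 180 + 1 = 1
- R+181: 180 - 181 + 1 = 0
- R+182: 180 - 182 + 1 = -1
- R+186: 180 - 186 + 1 = -5
- R+190: 180 - 190 + 1 = -9

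Negative values begin at R+182. On the nominal schedule Visit 11 falls at R+187, so the lowest possible value is 180 - 187 + 1 = -6. With Visit 10 at the end of its window (R+186) and Visit 11 at EOT+10, collection reaches R+196 and the lowest value is -15.

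A participant with stays R+10 to R+15 and R+190 to R+194 gets 6 + (-9) = -3; the correct total is 6.

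Visit windowing does not remove all such records, since the analysis window for admissions in SAP Table 2 runs to day 186.

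**Overlapping records.**

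- Nested, R+10 to R+20 and R+14 to R+17: 11 + 4 = 15, against 11 distinct days.
- Transfer entered as two stays, R+10 to R+15 and R+15 to R+20: 6 + 6 = 12, against 11 distinct days.

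**How many participants could have negative days (endpoint #8).** Inputs: six-month all-cause hospitalisation of 40% (SoC) and 16.2% (SZC) from protocol 9.2.2; about 130 randomised (65 per arm) and 104 evaluable (52 per arm) from protocol 4.1. Assumptions: constant hazard, and 7 days of late collection, R+181 to R+187. R+181 gives 0, so 6 of the 7 days produce negative values.

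- Daily hazard, SoC: -ln(0.60)/180 = 0.002838
- Daily hazard, SZC: -ln(0.838)/180 = 0.000982
- SoC: 65 × (1 - exp(-6 × 0.002838)) = 1.10; with 52, 0.88
- SZC: 65 × (1 - exp(-6 × 0.000982)) = 0.38; with 52, 0.31

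With 14 days of late collection (13 negative days) and 65 per arm, the same formula gives 2.35 and 0.82. Endpoint #7 counts only HK-related stays, so its figures cannot be larger.

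The SZC figure carries the on-treatment rate into a period when SZC has been stopped. If the SZC arm instead had the SoC hazard after end of treatment, it would also have about 1.1 of 65.

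**Medians.** At the plan's rates about 65 × 0.60 = 39 SoC and 65 × 0.838 = 54 SZC participants have zero days. The median is the 33rd ordered value. Moving one or two participants below zero leaves it at 0 in both arms, and double-counted days affect only totals that are already positive.

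**The case against.** The strongest reply is that late admissions are already out of scope. The endpoint definition stops at 180 days, the derivation serves that definition, and a careful programmer would filter first. In #7, the restriction to relevant admissions might be read the same way. The SAP also reports the range, so a negative minimum would be visible.

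Part of this stands. The SAP does not intend to credit stays after day 180, and a reader who inferred such an intention would go too far. But the count endpoints carry the same 180-day limit in their definitions and still state the exclusion in their derivations. The truncation sentence deals with stays that run past day 180, not those that begin after it. In 4.2.15.2, the word relevant follows the adjudication of HK as a contributing factor and most naturally refers to that; 4.2.16.2 has no such word. Nothing in the 180-day limit addresses overlapping records.

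It is also fair to say that the documents do not show whether a transfer creates two eCRF records, and that 4.2.5.2 does not say whether a shared transfer date is an overlap. The transfer example is therefore conditional. The nested example is an overlap on any reading.

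A reader might further infer that the error dilutes a benefit of SZC, because late admissions should be commoner under SoC. The documents do not support a direction: SZC is discontinued at end of treatment and no off-treatment admission rate is given.

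**Conclusion.** The defect is real but small. As written, the derivations in 4.2.15.2 and 4.2.16.2 return negative days for starts at R+182 or later and count days more than once when records overlap. Under constant hazards, the plan's 40% and 16.2% rates and 7 days of late collection, about 1.1 SoC and 0.4 SZC participants of 65 per arm (0.9 and 0.3 of 52) would have negative days in endpoint #8. The SZC figure further assumes that the on-treatment rate persists after SZC stops. No frequency can be given for overlapping records.

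The mean, SD, range and Wilcoxon ranks are affected. It would be tempting to say that the medians are wrong too, but at the plan's own rates they stay at 0. Both endpoints are exploratory and outside the testing order in SAP Table 5, so no primary or secondary result changes.

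**What to change.** In both 4.2.15.2 and 4.2.16.2, add that only admissions with a start date on or before randomisation + 180 are included, and that overlapping records are merged before days are counted, so that each calendar day in hospital counts once. State explicitly that records sharing a transfer date are merged, because 4.2.5.2 does not settle that case. For #7, also say whether merging comes before or after the selection of stays with HK as a contributing factor.

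The cost is a sentence or two in each section and minor programming. No new data are needed. It should be settled before database lock.

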#### **4.2.16.3 Handling of Dropouts and Missing Data**

All available data on hospital admissions are to be used irrespective of intercurrent events, no adjustment is made for dropout.

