### **3.3.1.3 Handling of missing dates**

Incomplete dates (partial or missing dates where a full date is permissible) will be presented in the data listings as recorded on the eCRF. Missing hospital admission, emergency department and death dates will not be imputed. Every effort will be made to ensure complete information for these dates are available. However, for adverse event start and stop date and for prior and concomitant medication start and stop date, missing dates will be estimated as follows:

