#### **4.2.16.4 Primary Analysis of Exploratory Endpoint #8**

The total duration of LOS will be summarised as a continuous variable (mean, SD, median, range) by randomised treatment group in the FAS. A Wilcoxon rank-sum test by randomised treatment group will be used to calculate a two-sided p-value.

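### Both length-of-stay endpoints compare raw hospital days with no term for observed time, and a stay still open at loss to follow-up has no defined end

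*SAP*

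**What the plan says.** Endpoint #7 is total length of stay for admissions with hyperkalaemia as a contributing factor, and #8 is total length of stay for all admissions. Both have "Population: Full analysis set", so everyone randomised is included. Death and loss are labelled treatment policy. For #8, participants with "loss to follow-up prior to 180 days post-discharge will have all available hospital admission data used irrespective of the intercurrent event".

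Each stay is computed as "Min(Stop date of admission, Randomisation date + 180) – Start date of admission + 1". SAP 4.2.15.2 uses the same formula for #7, and "the total duration per participant will be calculated as the sum of all relevant hospital admissions". The drop-out rule, in the same words for both endpoints, is "All available data on hospital admissions are to be used irrespective of intercurrent events, no adjustment is made for dropout". For the comparison, "A Wilcoxon rank-sum test by randomised treatment group will be used to calculate a two-sided p-value". Additional analyses are marked not applicable for both (SAP 4.2.15.5 and 4.2.16.5).

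On dates, SAP 3.3.1.3 states: "Missing hospital admission, emergency department and death dates will not be imputed".

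The count endpoints on the same admissions are handled differently. They use time in study as an offset (SAP 4.2.5.4, 4.2.14.4). They trigger a mean cumulative count analysis if loss differs between arms by more than 10% (SAP 4.2.5.5, 4.2.14.5). They treat admissions as separate only when their dates do not overlap (SAP 4.2.5.2, 4.2.14.2).

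**The concern.** A participant lost on Day 10 with no recorded admission scores 0 days, the same as one known to be alive and at home for 180 days. One who dies on the third day of a first stay scores 3, which ranks better than a survivor discharged after 10. The score depends on how long a person was observed as well as on hospital use, and the Wilcoxon test cannot separate the two.

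The length-of-stay formula also has two gaps. It ends a stay only at the stop date or Day 180, so it does not say what to do with a stay still open at loss. It also adds 1 for every record and has no overlap rule.

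Healthcare resource use is the second goal in the protocol synopsis, and protocol 2.1 says the results may support health technology assessment. The trial is open-label with 20% post-randomisation drop-out planned, so unequal loss is possible.

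**Working it through.** **The plan's own figures.** The documents give no power or expected value for length of stay. The sample size for the main secondary endpoint (protocol 9.2.2) reproduces and sets the scale. HR = ln(0.83)/ln(0.568) = 0.329. Freedman's formula at 5% two-sided and 80% power gives 31 events. With mean event probability (0.17 + 0.432)/2 = 0.301, 31/0.301/2 = 51.5, rounded up to 52 per arm. Then 104/0.8 = 130 randomised, or 65 per arm.

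**Effect of unobserved time on the mean.** If losses are spread evenly over 180 days, each lost participant loses half the follow-up on average. With equal true hospital use, 10% loss lowers observed mean days by 0.10 × 0.5 = 5%, and 30% loss by 0.30 × 0.5 = 15%.

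**Effect on the Wilcoxon test.** I simulated the SAP formula with 65 per arm, 3,000 trials per scenario and the same admission process in both arms. The following inputs are assumptions:

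- 43.2% of each arm would have at least one admission in 180 days. This borrows the plan's SoC composite rate. With gamma frailty of variance 1, it means 0.432/0.568 = 0.76 admissions per 180 days.
- Stays are exponential with mean 8 days.
- Loss is exponential and unrelated to outcome.
- A stay open at loss ends at loss.

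| Loss (arm 1/arm 2) | Mean days | Significant for arm 1 | Significant for arm 2 |
|---|---|---|---|
| 20%/20% | 5.5 v 5.5 | 2.3% | 2.9% |
| 25%/15% | 5.3 v 5.7 | 4.4% | 1.7% |
| 30%/10% | 5.2 v 5.9 | 6.7% | 0.7% |
| 40%/0% | 4.8 v 6.2 | 15.5% | 0.3% |

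The nominal rate is 2.5% on each side. The simulation error at that rate is √(0.025 × 0.975/3000) = 0.3 percentage points. At 30%/10%, 62.4% and 58.5% of participants score zero. Dividing hospital days by observed follow-up gives 6.2 days per 180 in both arms, so the exposure term removes the difference.

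**The open stay.** Count days from randomisation. An admission on Day 100 last seen on Day 110 has 110 − 100 + 1 = 11 observed days. If the stop date is blank and the minimum is taken over non-missing values, as the SAS MIN function does, the formula gives 180 − 100 + 1 = 81. A programmer who treats the result as missing would drop the stay.

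**Direction of that gap.** Re-running 30%/10% with open stays extended to Day 180 narrows the means to 5.9 v 6.1 days. The rate favouring the higher-loss arm falls from 6.7% to 6.2%.

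**Overlap.** A transfer on Day 20, entered as Days 15 to 20 and Days 20 to 25, gives 6 + 6 = 12 days for 11 calendar days.

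**The case against.** Several stronger readings are tempting, and the documents do not support them.

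- A reader might infer that the missing cap at death or last contact is what favours the arm with more losses. It is not: a missing cap can only lengthen a stay, so it works against that arm.
- A reader might infer that early death or drop-out is ranked as the best outcome. Zero days requires that no admission was recorded first, and it is a tie with event-free completers. The protocol synopsis treats death without prior hospitalisation or ED visit as negligible. That covers neither drop-out nor death after a short stay.
- A reader might infer that the planned 20% drop-out distorts the comparison by itself. The plan gives no split by arm, and at 20%/20% the test kept its level.
- The SAP gives an algebraic formula, not code. Filling a blank stop date with Day 180 would sit badly with the ban on imputing, and the SAP promises every effort to obtain complete dates. The open stay is therefore an ambiguity, not a specified error.
- The documents do not say that transfers are entered as separate records, so double counting is conditional on that.

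The plan also limits loss. Participants who stop treatment stay in follow-up (protocol 7.1.1), those considering withdrawal are offered contact through relatives, physicians or records (protocol 7.2), and chart review supplements visits (protocol 8.8.1). Disposition is reported by arm (SAP 4.1.1.2). These measures reduce the likely size of the problem but do not supply an analysis for whatever loss remains. Finally, both endpoints are exploratory and outside the testing order in SAP Table 5, and resource use is also assessed through secondary endpoints, including offset-adjusted counts.

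**Conclusion.** The point holds as a cheap improvement. Scoring unobserved time as zero days can favour the arm with more losses, but only when loss is unequal. Under the assumptions above, the effect is absent at equal loss, modest at a 10-point difference and clear at 20 points or more. The sizes depend on assumed admission rates, stay lengths and non-informative loss; the direction follows from the definition. The SAP foresaw unequal loss for the count endpoints and left length of stay without an equivalent analysis.

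The undefined end of an open stay is a separate specification gap that pushes the other way, with 81 against 11 days in the worked example. The missing overlap rule is a third, smaller gap. None of these affects a confirmatory claim.

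**What to change.** Keep the Wilcoxon analysis, which protocol 9.4.3.3 specifies, and add the following for both endpoints:

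1. An exposure-adjusted analysis, for example a negative binomial model of hospital days with log observed time as offset, where observed time ends at the earliest of death, last contact or Day 180.
2. A derivation that ends each stay at the earliest of stop date, death, last contact or Day 180, with an explicit statement that this covers blank stop dates.
3. A count of distinct calendar days, so that overlapping or same-day records add each day once.
4. Numbers of deaths and losses by arm, shown beside the length-of-stay results.

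Ranking deaths worst, or days alive and out of hospital over observed time, could be an optional sensitivity analysis. Neither should replace the planned analysis. Days alive and out of hospital to a fixed Day 180 would leave drop-out unsolved, because days after loss are not observed. The offset itself corrects for unequal observation time, not for loss related to prognosis.

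The cost is a little extra programming and a note in SAP section 2 recording the addition to the protocol's analyses. The data are already collected.
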